**Influenza-like illness (ILI) resolution** is defined as the first day when the following conditions are met simultaneously: temperature  $< 37.5^{\circ}\text{C}$  ( $< 99.5^{\circ}\text{F}$ ) with no fever reducers used, other symptoms (cough, sore throat, nasal congestion, rhinorrhea, earache

or ear discharge) either absent or mild, and a return of the child to normal activities (Jacobs, 2000) (Shepperd, 2004).

**Influenza confirmed case:** RT-PCR confirmed influenza in a subject who meets the criteria for protocol defined ILI.

**Legally Acceptable Representative(s):** An individual or juridical or other body authorized under applicable law to consent, on behalf of a prospective subject, to the subject's participation in the clinical trial (see ICH-GCP, ICH E6 (R2)).

**Lower respiratory tract illness:** Defined as either shortness of breath, pulmonary congestion, pneumonia, bronchiolitis, bronchitis, wheezing, or croup.

**Medically attended visit:** Defined as a hospitalization, emergency room/ department visit or a visit to/ by a healthcare provider for symptoms or illnesses. Scheduled clinic study visits and unscheduled study visits related to protocol defined ILI are not part of this definition.

**Qualified healthcare professional:** Any licensed health care professional who is permitted by institutional policy to perform clinical interventions and assessments such as physical examinations, is trained on the study procedure(s) and who is identified within the site signature and delegation log.

**Moderate-to-severe ILI episode:** ILI episode complicated by one of the following: physician confirmed lower respiratory tract illness, physician confirmed acute otitis media, or hospitalization in the Intensive Care Unit (ICU), physician-diagnosed serious extra-pulmonary complication of influenza or supplemental oxygen requirement for more than 8 hours.

**New onset of ILI episode:** As a guidance, another episode and swab sample should only be collected when the interval between the onset of protocol defined ILI to the next onset of protocol defined ILI is 14 days or more.

**Not-previously influenza vaccinated subject:** A subject that has not received 2 or more doses of influenza vaccine prior to the current influenza season, or who does not know the influenza vaccination history.

**Previously influenza vaccinated subject:** A subject with a known history of at least 2 influenza doses prior to the current influenza season.

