### **5.4.2 Unscheduled Visit(s)**

An unscheduled visit describes a non-routine study visit triggered by a specific event: (onset of) ILI symptoms during active ILI surveillance

Subject will be asked to come to the study site for an unscheduled visit within the first 24 hours or as soon as possible following ILI onset to ensure optimal viral yield. Preferably, samples will be accepted if collected up to 6 days following the day of ILI onset. In the exceptional case that a clinic visit is not feasible, a home visit may be considered.

The following procedures should be carried out during this unscheduled visit:

- a) The ILI symptoms and ILI Booklet will be reviewed and collected. The information should be mentioned in the subject's source documentation and recorded on the ILI event eCRF.
- b) Subjects meeting the protocol defined criteria for ILI will have a nasopharyngeal (NP) swab collected for evaluation for the presence of influenza virus. A NP swab is strongly preferred sampling method to ensure consistency across the study population (see Clinical Specimen Lab Manual for detailed procedures for collecting, processing and shipping ILI swab samples). NP swabs should be taken prior to antiviral therapy.

If an antiviral therapy has been given prior to swab sampling, this should be mentioned in the subject's source documentation and recorded on the Concomitant Medication page in eCRF. Subjects with ILI symptoms and its complications ought to be treated according to recent accepted (national) clinical standards.

- c) The Investigator will record the subjects body temperature as part of the Physical Examination (see [Section 5.1.2, Screening](#)).
- d) Physical examination findings will be recorded in the medical source documents and Adverse Events eCRF.
- e) The use of relevant medications and the occurrence of medically-attended AEs within 30 days after the onset of ILI episode will be assessed.
- f) ILI Symptom Assessment and Documentation Training including an ILI Booklet will be provided (see [Section 5.2.5, ILI Symptom Assessment and Documentation](#))

The site should schedule the ILI follow-up call with the subject's parent(s)/LAR.

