### 7.1.2 Unsolicited Adverse Events

All unsolicited adverse events need to be collected during the treatment period, which from informed consent to visit 2 for subjects with a history of previous influenza vaccination, or visit 3 for subjects with an unknown or without an influenza vaccination history (see [Time and Event Table](#)). During the follow-up period, from visit 2 or visit 3 respectively depending on previous influenza vaccination history up to the study completion visit, only those unsolicited adverse events that either are medically-attended AEs occurred within 30 days after the onset of ILI episode, or lead to withdrawal or are Serious Adverse Events, need to be reported on the Adverse Events eCRF (see [Time and Events Table](#)).

An unsolicited adverse event is an adverse event that was not solicited using a subject diary card and that was spontaneously communicated by a subject's parent(s)/LAR who has signed the informed consent.

Potential unsolicited AEs may be medically-attended (defined as symptoms or illnesses requiring hospitalization, or emergency room visit, or visit to/by a health care provider), or were of concern to the subject's parent(s)/LAR. In case of such events, subject's parent(s)/LAR will be instructed to contact the site as soon as possible to report the event(s). Unsolicited AE may also be reported during post-vaccination clinic visits or safety assessment phone calls. The detailed information about the reported unsolicited AEs will be collected by a qualified health care professional during the interview and will be documented in the subject's source records. Depending on the timing and nature of the event, the AE should be reported in the AE CRF (see [Section 7.1.3, Evaluation of Adverse Events](#), [Section 7.1.4, Serious Adverse Events](#), and [Section 7.1.5, Methods for Recording Adverse Events and Serious Adverse Events](#)).

An unsolicited AEs may be worsening of symptoms or illnesses reported in the Medical History eCRF (see [Section 5.1.2, Screening](#)).

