### 7.1.3 Evaluation of Adverse Events

Every effort should be made by the investigator to evaluate safety information reported by a subject for an underlying diagnosis and to capture this diagnosis as the event in the AE page. In other words, the practice of reporting only symptoms (e.g., "cough" or "ear pain") are better reported according to the underlying cause (e.g., "asthma exacerbation" or "otitis media").

The severity of events reported on the Adverse Events eCRF will be determined by the investigator as:

Mild: transient with no limitation in normal daily activity.  
Moderate: some limitation in normal daily activity.  
Severe: unable to perform normal daily activity.

The relationship of the study treatment to an AE will be determined by the investigator based on the following definitions:

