6.7.1.3 Analysis of Unsolicited Adverse Events

Definitions

All AEs will be characterized according to the date of occurrence related to the first vaccination as follows:

- **Non-Treatment Emergent:** start date before the date of first injection of study vaccine. These are reported in the Medical History output.
- **Treatment Emergent:** start date on or after the date of injection of study vaccine or, AE increase in severity, including to "serious" AE.

If start date is equal to the first date of injection, then "timing" variable ("Did event start before or after vaccination?") will be used to define whether the AE occur before or after the injection.

If an AE happened on the same day of first injection and the time stamp is missing, then the AE is assumed to be treatment emergent.

If an AE start date is missing or unknown, the AE will be considered as emergent.

When start and/or end dates of an AE are only partially known, AEs will be categorized as emergent before, during, or after vaccination phase using the following rules:

- If the partial end date is before ($<$) the first vaccination (i.e., year or year & month is/are before the first study vaccination year or year & month) then the AE is not treatment-emergent.
- If the partial start date is equal or after (\geq) the first study vaccination (i.e., year or year & month is/are after or the same as the first study injection year or year & month) then the AE is considered treatment-emergent.

The **maximum event severity** is the greatest severity associated with a preferred term (PT) for a reported AE according to the following order: Mild < Moderate < Severe. Unknown/ Missing severity is considered as severe.

Multiple AEs with the same PT for the same subject are counted only once.

Vaccination-related AEs are those for which the cause has been evaluated by the investigator, and recorded as related.

Analysis of Unsolicited Adverse Events

This analysis applies to all Treatment Emergent adverse events occurring during the study, judged either as probably related, possibly related, or not related to vaccination by the investigator, recorded in AE Case Report Form (CRF), with a start

Statistical Analysis Plan – Final v2.0

Sponsor Name: Seqirus UK Limited
Sponsor Protocol ID: V130_14

date on or after the date of first vaccination. AE starting prior to the first vaccination will be reported in the Medical History output.

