The original verbatim terms used by investigators to identify AEs in the CRFs will be mapped to preferred terms using the Medical Dictionary for Regulatory Activities (MedDRA) dictionary. The AEs will then be grouped by MedDRA preferred terms into frequency tables according to SOC. All reported AEs, as well as AEs judged by the investigator as at least possibly related to study vaccine, will be summarized presenting the number and percentage of subjects having one or more events according to system organ class and preferred term within system organ class. These summaries will be presented by vaccination group and period (as defined in section 2.2): treatment period, follow up period and total observation period (Day 1 until study end). When an AE occurs more than once for a subject, the maximal severity and strongest relationship to the vaccine group will be counted.

Separate summaries will be produced for the following categories:

- SAE
- NOCD
- Adverse events/Serious Adverse events that are possibly or probably related to vaccine
- Adverse event leading to study withdrawal or early termination
- Adverse events leading to a medically-attended visit within 30 days after the onset of ILI episode
- Adverse events leading to a medically-attended visit during the treatment period
- Adverse event resulting in death

Data listings of all adverse events will be provided by subject. In addition, adverse events in the categories above will be provided as listed data.

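### Protocol rules conflict on which ILI-visit findings become AE entries, and SAP 6.7.1.3 does not separate them, so efficacy can lower QIVc's follow-up and total-period AE counts

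*Protocol*

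**What the plan says.** Protocol 5.4.2 gives ILI visits two recording routes. Under item (a), ILI symptoms and booklet information are "recorded on the ILI event eCRF". Under item (d), "Physical examination findings will be recorded in the medical source documents and Adverse Events eCRF". Item (d) has no limit by study period, severity or swab result, and Protocol 5.4.1 runs surveillance from Visit 1 to the end of the season.

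For follow-up, Protocol 7.1.2 is narrower. The entries required on the AE eCRF are "only those unsolicited adverse events that either are medically-attended AEs occurred within 30 days after the onset of ILI episode", plus AEs leading to withdrawal and SAEs. The List of Definitions adds, for a medically attended visit: "Scheduled clinic study visits and unscheduled study visits related to protocol defined ILI are not part of this definition". Protocol 7.1.3 defines a medically-attended AE without repeating that exclusion. It also tells investigators to look for the underlying diagnosis and "to capture this diagnosis as the event in the AE page".

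On analysis, SAP 6.7.1.3 states: "This analysis applies to all Treatment Emergent adverse events occurring during the study". Summaries are by vaccination group for the "treatment period, follow up period and total observation period (Day 1 until study end"). Separate summaries cover SAEs, NOCDs, withdrawals and medically-attended AEs within 30 days of ILI onset. Neither document removes or separates ILI-linked events in the general tables. Protocol 7.1.5 only exempts RT-PCR confirmed influenza in QIVc recipients from expedited reporting.

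**The concern.** There are two linked problems.

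The first is data capture. In follow-up, a site that follows 5.4.2(d) enters abnormal findings from an ILI visit as AEs. A site that follows 7.1.2 with the List of Definitions leaves most of them out. A site that relies on 7.1.3 alone could count the ILI visit itself as medical attendance. The number of AE entries then depends partly on which section a site reads.

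The second is interpretation. Confirmed influenza is the efficacy outcome. Where it or its findings reach the AE eCRF, an effective vaccine produces fewer AE entries for a reason unrelated to its safety. The by-arm follow-up and total-period tables then mix efficacy with safety, mainly in the rows for any AE, respiratory disorders and infections.

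**Working it through.** **Inputs from the documents.** Protocol 8.5 and SAP 2.3 give a comparator attack rate of 8%, VE of 40%, one-sided α of 0.0125, 90% power, and a QIVc safety set of 1,723. The implied QIVc attack rate is 0.08 × 0.6 = 4.8%.

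**The plan's own figures reproduce.** Events for endpoint 1a: 4 × (2.2414 + 1.2816)² / (ln 0.6)² = 190.25, rounded up to 191. Evaluable subjects: 190.25 / [(0.08 + 0.048)/2] = 2,972.7, rounded up to 2,974 for equal arms. For the safety set, 1 − (1 − 1/1,000)^1,723 = 82.2%, as stated.

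**Carry-over formula.** Let c be the share of influenza cases that reach the AE eCRF and b the share of children with some other AE in the table. The documents give neither. I assume both are the same in each arm and independent of each other. The proportion with at least one AE is:

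- comparator: 1 − (1 − b)(1 − c × 0.08)
- QIVc: 1 − (1 − b)(1 − c × 0.048)

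The difference is D = (1 − b) × c × 0.08 × VE.

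**Ceiling (c = 1, b = 0, VE 40%).** D = 0.08 × 0.40 = 3.2 points. At 1,723 per arm this is 137.8 against 82.7 children, or about 55. This case also describes a single influenza preferred-term row: 8.0% against 4.8%, ratio 1.67.

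**Dilution by other AEs (c = 1, VE 40%).** The last column shows how visible the difference would be. The plan specifies no such test.

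| b (assumed) | D, points | Chance of nominal two-sided p < 0.05 |
|---|---|---|
| 0% | 3.2 | 97% |
| 20% | 2.6 | 41% |
| 40% | 1.9 | 21% |
| 60% | 1.3 | 12% |

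**If 7.1.2 governs (VE 40%, c assumed 10–50%).** With b = 0, D runs from 0.10 × 3.2 = 0.3 to 0.50 × 3.2 = 1.6 points. With b = 40%, it runs from 0.6 × 0.32 = 0.2 to 0.6 × 1.6 = 1.0 points. The overall range is about 0.2 to 1.6.

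**Dependence on efficacy (c = 1, b = 0).** D is 0, 1.6, 3.2 and 4.8 points at VE 0%, 20%, 40% and 60%.

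**What adds nothing.** Influenza-negative ILI should be about equal in the two arms and so creates no difference.

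**Why the treatment period is less exposed.** It ends 28 days after the last dose. The plan counts cases only from more than 14 days after that dose, because protection is not immediate. The overlap is therefore about two weeks. It is not nil, since ILI surveillance starts at Visit 1.

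**The case against.** A fair defence makes five points.

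- **Not every ILI visit creates a tabulated AE.** A reader might infer that it does from 5.4.2(d) alone. But symptoms go to the ILI event eCRF, Protocol 5.1.2 asks for eCRF entry of abnormal findings, 7.1.3 prefers a diagnosis to symptoms, and SAP 6.7.3 only lists physical findings. This stands. The listing does not, however, remove entries already made on the AE eCRF.
- **Much of the needed separation exists.** The protocol's unsolicited-AE endpoint stops 28 days after each vaccination, the treatment period is shown apart, and one safety endpoint is openly built on ILI onset. This stands. The gap is confined to the general follow-up and total-period tables.
- **Masking is limited.** A reader might infer that a true excess of other AEs could be hidden generally. AEs are shown by system organ class and preferred term, so influenza or otitis rows cannot hide an excess in unrelated terms. Only an any-AE row or a shared organ-class row can do so. There is also no safety hypothesis or success criterion.
- **Inclusion is not an error in itself.** Protocol 7.1 counts intercurrent illness as an AE, so less influenza under QIVc is a real difference. This stands, but readers still need to see how much of a difference comes from that source.
- **The AE eCRF serves efficacy too.** Protocol 7.2 builds moderate-to-severe influenza from medically-attended AEs reported in the eCRF. Moving ILI-visit findings wholesale to the ILI form could lose complications that feed that endpoint. This stands and constrains the fix.

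**Conclusion.** The point holds in a limited form. The recording rules conflict for the follow-up period. The SAP's follow-up and total-period AE tables mix ILI-linked events with other AEs, in a direction that lowers QIVc counts if VE is above zero.

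A reader might take 3.2 points as the expected bias, or conclude that QIVc's whole safety profile will look better than it is. The documents support neither. The 3.2 points is a ceiling at VE 40% that needs every influenza case to yield an AE entry and no child to have another AE. Other AEs, or enforcement of 7.1.2, reduce it to the smaller figures above. The capture share and background AE rate are assumptions. Background may be low in follow-up, where only selected AE categories are collected, so dilution should be weakest there.

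The matter merits correction because it affects by-arm safety tables and consistency between sites. It does not affect the primary efficacy analysis.

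**What to change.** **Protocol.** Reconcile 5.4.2(d) with 7.1.2, the definition of a medically attended visit, and 7.2, so that one rule says which ILI-visit findings become AE entries in each period. The rule must keep on the eCRF every physician-confirmed complication that feeds the moderate-to-severe endpoint, including one confirmed only at the ILI study visit. Use the same wording on medical attendance in 7.1.3.

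**SAP 6.7.1.3.** Flag AEs linked to a protocol-defined ILI or confirmed influenza, with the linking rule fixed before unblinding. Present the follow-up and total-period by-arm tables with and without flagged events. Limit follow-up tables to the categories collected then: SAEs, AEs leading to withdrawal, medically-attended AEs within 30 days of ILI onset, and NOCDs (collected under Protocol 3.1, though 7.1.2 omits them).

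**Cost.** Wording changes in both documents, one linking flag, and one more split in the AE tables.

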### **5.4.3 ILI Follow-up Call**

An ILI follow-up call will be performed at 30 (+7) days after protocol defined ILI onset, amongst subjects who have had their NP swab obtained. The subject's parent(s)/LAR will be asked a set of questions to:

- a) Assess ILI symptoms and associated medications, if any.
- b) Assess medically-attended adverse events within 30 days after protocol defined ILI.
- c) Remind subject of next study activity.

The subject's parent(s)/LAR will be reminded to contact the site if there are any questions and to contact the site immediately (or as soon as the subject is medically stable) if the subject has a medical condition that leads to a hospitalization or an emergency room visit. Both contact and the medical condition/event must be documented in the subject's source record.

In countries, in the exceptional case where calls are not feasible, study site personnel may visit the subject's homes to inquire about signs and symptoms of illness in the subject.

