
Name of Sponsor:
 
Seqirus
	
Protocol number:
 
V130_14
	
Generic name of study vaccine(s):
 
Cell-Based Quadrivalent Subunit Influenza Virus Vaccine (QIVc)
 
Non-Influenza Vaccine

Follow-up period: During the follow-up period, safety data including ‘AEs leading to withdrawal’, ‘SAEs’, ‘NOCs’, ‘medically-attended AEs until 30 days after ILI onset’ and all medications used related to these events will be captured. In case of such events, subject’s parent(s)/LAR will be instructed to contact the site as soon as possible to report the event(s). Furthermore, a safety follow-up call 90 days after last vaccination will be performed.
 
During treatment and follow-up period: Unscheduled visits are planned for subjects who manifest signs of influenza-like illness (ILI) during the influenza season and will be evaluated by testing of a nasopharyngeal (NP) specimen for influenza. Thirty (30) days after ILI onset, an ILI follow-up call with associated checklist will be performed to determine if subsequent medically-attended adverse events occurred including concomitant medication associated with these events.
 
After enrollment, a weekly alert (for example a telephone call) will serve as a reminder to the subject’s parent/LAR/designate to report ILI symptoms to the study investigator. Subjects with ILI symptoms and its complications ought to be treated according to recent accepted (national) clinical standards. Subject’s parent(s)/LAR will be asked to contact the site immediately if health concerns arise.
 
At the end of influenza season but at least 180 days after last vaccination date:
 
A scheduled study visit 5 (clinic / home visit or call) at the end of influenza season but at least 180 days after last vaccination will occur. All subjects aged 6 through 11 months will receive a MenC vaccination, regardless of treatment assignment.
 
In countries, where the MenC vaccine (Neisvac-C, Pfizer) is not licensed, an extra visit (Visit 6) is performed, only to assess the safety of the MenC vaccine at approximately 28 days after vaccination at Visit 5.
		

Study Vaccines and Schedule:
 
Investigational vaccine: The investigational vaccine is Flucelvax Quadrivalent/Flucelvax Tetra (QIVc, Seqirus), and contains 0.5 mL including 15 µg purified viral
		

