### **5.3.2 Safety Follow-up Visit**

The Safety Follow-up visit is a telephone call performed 90 days after last vaccination (e.g. Visit 3 or Visit 4, depending on influenza vaccination history). In countries, in the exceptional case where calls are not feasible, appropriate study site personnel may visit the subject's homes to inquire about signs and symptoms of illness in the subject.

Safety follow-up calls are calls made to the subject's parents(s)/LAR by qualified health care professional designated on the site's roles and responsibilities log. These calls will follow a script which will facilitate the collection of relevant safety information. The subject's parent(s)/LAR will be interviewed according to the script, and information relating to unsolicited adverse events including: serious adverse events (SAEs), new onset of chronic disease (NOCD), all medically-attended AEs within 30 days after the onset of ILI episode, and/or AEs leading to withdrawal, and concomitant medications or vaccinations associated with those events. All safety information described by the subject must be written down in a designated location within the source document and not written on the script used for the telephone call. The script will also include a question on ILI occurrence.

The site should schedule the next safety follow-up call (if applicable) with the subject's parent(s)/LAR.

The subject's parent(s)/LAR will be reminded to contact the site if there are any questions and to contact the site immediately (or as soon as the subject is medically stable) if the subject has a medical condition that leads to a hospitalization or an emergency room visit

or to a visit to/by a doctor. Contact including the medical condition/event must be documented in the subject's source record.

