If during the study completion visit, ILI symptoms are reported by the parent/LAR and if the onset of the ILI is within ( $\leq$ ) 6 days before the study completion visit, an NP swab should be collected from the subject for influenza testing and study staff will document the ILI in the subject's source records and on the ILI eCRF (see procedures described in [Section 5.4.2 Unscheduled Visit\(s\)](#)). Should an ILI be identified and a NP swab taken, it is recommended to postpone the study completion visit, to allow for the ILI follow-up visit to occur. In these instances, missing the study completion visit window is not considered a protocol deviation. Should the subject have experienced a protocol defined ILI for which an NP swab was obtained, please collect the information of any medically-attended adverse events which have occurred within 30 days after the onset of the of ILI. If study completion is after the end of influenza season (i.e. after active ILI surveillance), documentation of an ILI and collection of a swab is not applicable.

For subjects who will receive a dose of the MenC vaccine (see [Section 6.2, Vaccine Preparation and Administration](#)) during Visit 5, the vaccine is administered according to the procedures described in [Section 6.2, Vaccine Preparation and Administration](#), and the subject will be observed for at least 30 minutes.

The site will review with the subject's parent(s)/LAR the plan of when information relating to the subject's participation in the study may be available (e.g., study results, treatment assignments). It will also be discussed how information relating to the subject's participation in the study will be shared with the subject's healthcare provider, if the subject's parent(s)/LAR chooses to share this information.

The site will complete the study completion eCRF page and this will mark the completion of the subject's participation in the study.

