#### **8.1.2 Secondary Endpoint(s)**

##### **8.1.2.1 Secondary Safety Endpoint(s)**

The measures for assessing safety and tolerability are as follows:

1. Percentage of subjects with solicited local and systemic AEs will be assessed for 7 days following each vaccination in the QIVc group and the comparator group.
2. Percentage of subjects with any unsolicited AEs will be assessed in the QIVc group and in the comparator group until 28 days after each vaccination.

3. Percentage of subjects with SAEs, NOCDs, AEs leading to withdrawal from the study or vaccination, and all medications associated with these events will be reported in the QIVc group and in the comparator group.
4. Percentage of subjects with medically-attended AEs within 30 days after ILI onset will be reported in the QIVc group and in the comparator group.

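### Safety endpoint 4 covers every ILI, but Section 5.4.3 limits its 30-day follow-up call to swabbed children, so events after unswabbed ILIs are collected later and depend more on recall

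*Protocol*

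**What the plan says.** **The endpoint.** Protocol Section 8.1.2.1, item 4, repeated in SAP Section 3.2: "Percentage of subjects with medically-attended AEs within 30 days after ILI onset will be reported in the QIVc group and in the comparator group". Neither place mentions a swab.

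**The call.** In the protocol synopsis (Study Procedures), "an ILI follow-up call with associated checklist will be performed to determine if subsequent medically-attended adverse events occurred", again without a swab condition. Table 1.3 sets the call at ILI onset day +30. Its footnote mentions a swab only in connection with postponing the completion visit. Section 5.4.3 restricts the call to ILIs "amongst subjects who have had their NP swab obtained".

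**Study completion.** Section 5.5 first lists medically-attended events within 30 days of ILI onset among the items to be asked about in the completion interview, for all subjects. Its next paragraph asks for the same information under a condition: "Should the subject have experienced a protocol defined ILI for which an NP swab was obtained".

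**Swabbing.** Section 5.4.2 expects a swab for every qualifying illness: "Subjects meeting the protocol defined criteria for ILI will have a nasopharyngeal (NP) swab collected". The same section tells the site to schedule the follow-up call and attaches no swab condition to that instruction.

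**The concern.** The endpoint is defined on ILI onset. The one contact timed to the end of its 30-day window is defined on having been swabbed. An ILI can meet the definition and still go unswabbed. The family may not attend, or the illness may come to light too late: samples are preferably taken within 6 days of onset, and Section 5.5 directs a swab at completion only if onset was no more than 6 days before. Reading Section 5.4.3 literally, a site would make no 30-day call for such a child, while a site following the synopsis would.

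The completeness and consistency of a named safety endpoint are at stake. The gap would also be hard to see in the analysis. SAP Section 5.2 does not impute adverse events, and SAP Section 4.3 keeps assessed subjects with no recorded event in the Unsolicited Safety Set. An event that no route picks up is therefore counted as no event. The SAP does report missing safety calls and assessments, but a call that Section 5.4.3 does not require may not count as missing.

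**Working it through.** The plan gives no figure that depends on this point, so there is nothing to reproduce. The check has two parts.

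**1. Routes open after an unswabbed ILI**

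| Route | Source | What it covers |
|---|---|---|
| Collection of all unsolicited AEs | Protocol 7.1.2 | Up to the visit 28 days after last vaccination |
| Day-90 safety call | Protocol 5.3.2 | All subjects; asks about "all medically-attended AEs within 30 days after the onset of ILI episode" |
| Completion interview | Protocol 5.5 | All subjects in one paragraph, swabbed ILIs in the next |
| SAE reporting | Protocol 7.1.4, 7.1.5, Table 1.1 | Any time in the study, including hospitalizations |
| Parent-initiated report, entered as a reportable AE | Synopsis; Protocol 3.8, 5.3.2, 7.1.2 | Any time, if the parent makes contact |

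The unscheduled visit (5.4.2) also assesses these events, but its window is day 0 to +6 after onset, so it cannot see most of the 30 days. The weekly reminder calls are not meant to collect clinical data (5.4.1).

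*Timing.* The day-90 call sees a complete 30-day window only if onset was by day 90 - 30 = 60 after last vaccination. For later onsets, the window is still open at the call or has not begun. The next scheduled contact that asks about these events is study completion, at day 180 or later. For onset on day 61, the window closes on day 91, and the interview comes at least 180 - 91 = 89 days after that. This is the period in which collection is weakest, and it leans on the section whose two paragraphs disagree.

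**2. Illustrative size**

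Let u be the share of true endpoint-4 events that follow unswabbed ILIs, and c the share of those caught by the routes above. Assume complete capture after swabbed ILIs and one relevant ILI per subject.

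- Share captured = (1 - u) + u·c
- Relative loss = 1 - [(1 - u) + u·c] = u(1 - c)

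The documents give neither u nor c. With assumed values:

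| u | loss at c = 0.5 | loss at c = 0.9 |
|---|---|---|
| 5% | 0.05 × 0.5 = 2.5% | 0.05 × 0.1 = 0.5% |
| 10% | 0.10 × 0.5 = 5% | 0.10 × 0.1 = 1% |
| 20% | 0.20 × 0.5 = 10% | 0.20 × 0.1 = 2% |
| 30% | 0.30 × 0.5 = 15% | 0.30 × 0.1 = 3% |

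**The case against.** The strongest reply is that the call is one route among several. The day-90 script and the completion interview name exactly this event category for all subjects. Section 7.1.2 makes these events reportable throughout follow-up, and Section 3.8 sends them to the AE page after any protocol-defined ILI. Unswabbed ILIs should also be uncommon: surveillance is weekly, the 6-day limit is a preference, home visits are allowed, and nasal or oropharyngeal swabs are accepted alternatives. The synopsis sentence on the call follows directly after one on swab testing, so a swab may be implied there. The swab sentence in Section 5.5 may be meant only as an added reminder. The endpoint is descriptive, with no success criterion (8.2.2.1) and no hypothesis (8.4.3.1.4).

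Most of this stands, and it rules out two stronger readings.

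- A reader might infer that unswabbed ILIs are in effect scored as event-free. That would need c = 0, which the other routes contradict.
- A reader might infer that the more serious events are the ones lost. Hospitalizations are SAEs, to be reported within 24 hours of site awareness whatever the swab status, so they have an additional route. The documents do not say that sicker children are swabbed less often.

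The reply does not remove the conflicting instructions in the synopsis and Sections 5.4.2, 5.4.3 and 5.5. Nor does it make an interview months later equivalent to a call at day 30.

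**Conclusion.** The point holds as one of completeness and consistency of collection. A named safety endpoint applies to all ILIs, its dedicated call applies to swabbed ones, and the protocol disagrees with itself on the call and on the completion interview. After an unswabbed ILI, ascertainment is less complete and more dependent on recall, mainly when the 30-day window ends after the day-90 call.

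The size cannot be fixed from the documents. For u of 5-30%, the endpoint would be understated in relative terms by 0.5-3% if other routes catch 90% of the events, and by 2.5-15% if they catch half. Both u and c are assumptions.

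Two further inferences are not supported. Between-arm bias would need unswabbed ILIs, or the capture of events after them, to differ by arm, which the documents do not address. The RT-PCR endpoints, including moderate-to-severe influenza, are not affected by the call's swab limit, because a case needs a swab in the first place. This is an inexpensive improvement and does not threaten the trial's conclusions.

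**What to change.** Reconcile the synopsis and Sections 5.4.2, 5.4.3 and 5.5 (both paragraphs). The 30-day call and the collection at study completion should apply to every protocol-defined ILI identified during active surveillance, whether or not a swab was obtained. In the SAP, add a count by arm of ILIs without a completed 30-day assessment, so that the completeness of endpoint 4 can be judged.

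The cost is a wording change, one added SAP summary, and one scripted call per unswabbed ILI by staff already in weekly contact with these families.
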